Will pregnant women and/or fetuses (as described in 45 CFR 46 Subpart B) be enrolled in the research?

No

E4. Neonates

Will neonates of uncertain viability or nonviable neonates (as described in 45 CFR 46 Subpart B) be enrolled in the research?

No

E5. Children

Will children be enrolled in the research?

No

Section F: Design/Procedure

F1. Design

Select one category that most adequately describes your research:

z.r) Randomized, Efficacy Study -- Surgical Techniques/Interventions

Discuss the research design including but not limited to such issues as: probability of group assignment, potential for subject to be randomized to placebo group, use of control subjects, etc.

Overview. The goal of the study is to conduct and evaluate a time-limited, Veteran peer-support specialist-led navigation intervention on diabetes-specific outcomes, mental health outcomes, and use VHA or community care in Veterans with DM and clinically significant diabetes-related distress. We will evaluate the outcomes of the intervention in a randomized trial comparing the intervention to usual care. The proposed work is informed by an established and ongoing partnership between VHA researchers and clinicians, individual Veterans, and representatives of Veteran Service Organizations (VSOs)/Community Based Organizations (CBOs) serving Veterans. These key partners have been working together for more than a year, as described above, and will collaborate on all aspects of the research, as detailed below. Study design. This is a single-blind, parallel group, randomized trial of a 3-month peer-navigation intervention for Veterans with DM and elevated levels of diabetes-related distress. Participants will be assigned at random (see below) to the intervention (peer navigation with follow-up) or usual care (print materials and encouragement to continue follow-up with health care providers). Assessment of primary, secondary and intermediate end points will occur preintervention at baseline and postintervention at 3 and 6 months.

Participants. We plan to recruit 218 participants (1:1 allocation) over 31 months (7/month). Central to the design of this trial is the recruitment of Veterans who are VHA users and Veterans who are not. We will screen at our local VHA medical center (MEDVAMC) and established community partnerships, including government agencies, CBOs, and VSOs as described above.

Inclusion Criteria:

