Patients will be eligible to participate in the study if they meet the following criteria:

(1) Veteran (2) Diagnosis of type 2 diabetes mellitus, per self-report (3) Moderate diabetes-related distress (Diabetes Distress Scale [DDS2] mean score of 3 or greater)

Exclusion Criteria:

(1) Lack of reliable access to a telephone (2) Cognitive, sensory, or other impairment that prevents use of a telephone (3) Current participation in another diabetes-related counseling or self-management program

F2. Procedure

Upon providing informed consent, participants will be randomized in blocks of 6 or 8, based on referral source (MEDVAMC and non-MEDVAMC). At the initial screen, the study staff will confirm eligibility. Veterans will be screened for distress using the 2-item screening version of the Diabetes Distress Scale. Veterans with a mean score of 3 or more will be eligible to continue. Veterans who are eligible and wish to participate further will be scheduled for a telephone baseline assessment. They will be mailed a cover letter, informed consent document without signature lines, and copies of baseline assessment instruments. A member of the study team will call and review the consent documents before final enrollment and completion of the baseline assessment.

Usual care. Veterans randomized to the usual care condition will be encouraged to follow-up with their primary care provider and/or specialty providers for management of their health conditions. They will receive a packet of printed information that includes a list of self-management support resources in the VHA and the local community, but no specific recommendations or referrals. The list will be updated periodically with similar resources as needed.

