
Peer coach selection and training. We will recruit two Veterans through referral from partner agencies and the VHA to serve as peer coaches. Recruitment, hiring, and interviewing will be based on the VHA's peer hiring toolkit. Peer coaches will not have other employment relationships with the VHA. Study investigators will provide 40 hours of training that will cover the role of a peer support provider, general principles of self-management, DM self-management, motivational techniques, goal setting, communication, safety issues and boundaries, and tracking and follow-up procedures. Included will be 8 hours of Military Veteran Peer Network Basic training provided by Mental Health America of Houston, which equips peer coaches with frontline intervention tools (e.g. modes of peer support; assessment skills; skills in handling suicide prevention, stress, and addictive behaviors). Peers will also be oriented to VHA and community DM and mental health resources. A study investigator-clinician readily accessible by phone will supervise coaches, meeting with each one at least weekly. Peers will be provided an intervention manual that includes safety guidelines.

Patient assessments will be measured by telephone by an independent evaluator without access to group assignments at baseline, M3 and M6: -Background and Demographics (baseline) -DM-related distress score, as measured using the DDS17 -Summary of Diabetes Self-care Activities Questionnaire (SDSCA) -The Patient Health Questionnaire-8 (PHQ-8) -The Generalized Anxiety Disorder-7 (GAD-7) -Veteran's self-report of use of community-based or VHA resources (baseline and M6) -Patient Activation Measure (PAM-13) -Patient-Reported Outcomes Measurement Information System (PCORI) instruments: Self-Efficacy for Managing Social Interactions, Emotions, and Daily Activities Participants will be asked if they would like to be mailed a summary of the study results after the study is completed.

Exit interview. We will administer a semistructured exit interview at M6 to intervention group participants to elicit patient-level barriers/facilitators to engagement and views on how to improve the intervention. Questions are designed to elicit

brief responses. Responses will be entered verbatim into the database.

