Outcomes: Primary outcome. We will compare participants in the 2 study arms on baseline characteristics, including sociodemographic characteristics and clinical variables. Based on the Consolidated Standards of Reporting Trials recommendations, we will not provide tests of significance or adjust subsequent analyses for variables found to differ because adjustment may bias the estimated treatment effect. However, because socioeconomic status (SES) and race/ethnicity might impact the mechanism of navigation/coaching, we will include the SES (income and education) and race/ethnicity variables as a priori covariates in our regression analyses. We will examine distributions of the primary outcome (DDS17) and consider transformations, if necessary. We will test for differences between the active intervention and usual care groups using continuous dependent measures (either untransformed or transformed if needed). The random coefficient model will allow us to fit a line for each participant using his/her available data, including participants with missing values, and will maximize the power to detect differences because participants are not removed from the analysis if any time period is missing. Analyses will contain a variable indicating the treatment group, a variable representing the referral source (MEDVAMC and non-MEDVAMC [community social service agencies, or VSOs]), SES and race/ethnicity variables, a variable indicating time (baseline, 3 months, or 6 months), and a term for the interaction of time and treatment. The time-by-treatment interaction is of most interest in this repeated measures analysis because a significant value will indicate a difference between groups over 6 months.

The treatment effect will measure differences between the groups at baseline, and the time effect will measure outcome change over time. By dichotomizing the outcome, we will determine whether the groups differed proportionally in clinically significant improvement on the DDS17. A value of 2.9 or less for the DDS17 will be considered as indicating little or no distress to moderate distress; a value of 3.0 or more will represent high distress. We will test this difference using a logistic regression model in which the dichotomous outcome is the dependent variable. Independent variables will be those for the linear regression models.

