Explain how the research involves no more than minimal risk to the participants, and the specifics demonstrating that the research does not involve procedures for which written consent is normally required outside of the research context.

We are requesting permission to verbally consent patient participants to this study by telephone. Given the intervention and research assessments are non-invasive in nature and almost exclusively involve monitoring and assessment of patient functioning, we have established telephone-based contact methods to decrease participant burden. To further improve this process we are requesting to verbally consent participants to afford us greater opportunities to increase our outreach to patients and decrease participant burden. Patients will be initially introduced to the study and screened by telephone. If the initial screen indicates the patient may be eligible for the study, the patient will be mailed detailed information about the study procedures and an informed consent document (without signature lines) for their review. The study coordinator or other research staff will then follow up with the patient by telephone. Telephone consent will occur before administering baseline measures. Our protections for confidentiality are described below. The telephone screening will be conducted using a structured script (attached in section S).

We are also requesting permission to waive written documentation of consent for stakeholder and research survey participation. The survey is a 28-item measure that includes items to describe engagement in the research process from the stakeholder point of view. The survey also asks for some basic demographic information including age, race, ethnicity, and gender. A cover page will include a description of the survey, potential risks, and a statement that participation is voluntary and refusal to participate will involve no penalty or loss of benefit. Survey responses will be anonymized prior to data analysis. Subjects can indicate with a check box if they consent or would like to opt out of participation. Details of stakeholder participation will also be explained in a brief Memorandum of Understanding.

J2. Consent Procedures

Who will recruit subjects for this study?

PI
PI's staff

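### Section F2 ties randomisation to consent, which precedes baseline, and nothing holds back the allocation until baseline DDS17 is recorded; if participants learn their arm first, the time-by-treatment test is exposed to bias

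*Combined protocol and SAP*

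**What the plan says.** - **Time of randomisation.** Section F2 gives the only statement: "Upon providing informed consent, participants will be randomized in blocks of 6 or 8", by referral source (MEDVAMC or non-MEDVAMC).
- **Consent and baseline.** F2 also says "A member of the study team will call and review the consent documents before final enrollment and completion of the baseline assessment". Section J1a agrees: "Telephone consent will occur before administering baseline measures". Section E2 gives the same order.
- **Timing of baseline.** Section F1 says "Assessment of primary, secondary and intermediate end points will occur preintervention at baseline and postintervention at 3 and 6 months". This places baseline before the intervention. It does not place it before randomisation.
- **Masking.** F1 states "This is a single-blind, parallel group, randomized trial". The only masking described is in F2: "Patient assessments will be measured by telephone by an independent evaluator without access to group assignments at baseline, M3 and M6".
- **Primary model.** Section G2 specifies a random coefficient model with "a variable indicating time (baseline, 3 months, or 6 months), and a term for the interaction of time and treatment". It adds: "The treatment effect will measure differences between the groups at baseline". The interaction is the test of main interest.
- **Covariates.** G2 includes income, education and race/ethnicity in the models. The F2 assessment list collects background and demographics at baseline only.

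**The concern.** If randomisation follows consent directly, an allocation exists before the first DDS17 is taken. DDS17 is the participant's own report. Someone who knows that a peer coach is coming, or that only printed material is, may rate distress differently from someone who does not know. A masked evaluator limits interviewer bias but cannot prevent this.

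Baseline is usually protected because it is measured before anyone can react to the assignment. Here it is also one of the three outcome times, and the arms are free to differ at it. A difference produced by knowledge of the arm would therefore be read as part of the change over time. It could go in either direction, and no later analysis could reliably separate it from chance imbalance.

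Other analyses in G2 rest on the same baseline reports. The PHQ-8 responder outcome is a decrease from baseline, and the new-use analyses select participants by non-use at baseline. Anyone randomised who never completes baseline would also lack the demographic covariates.

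**Working it through.** **Order of steps.** F2 has randomisation on consent. F2, E2 and J1a have consent before baseline. Taken together and literally, the order is consent, randomisation, baseline. No sentence states that full order, and none contradicts it.

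**The plan's own sample size, as a check on inputs (G1).** The inputs are d = 0.50, two-sided 0.05, 80% power, correlation 0.5, T = 2 and 30% attrition.
- Per arm at one time point: 2 × ((1.960 + 0.842)/0.5)² = 62.79
- Repeated-measures factor: [1 + (2 − 1) × 0.5]/2 = 0.75, giving 47.09
- Attrition: 47.09/0.70 = 67.28 per arm, against 67 per arm and 134 in total as stated

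The figure reproduces. The order of steps does not affect it, nor the increase to 218.

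**How a reporting shift enters the primary estimate.** Let s0 and s6 be the shifts, in SD units, that knowledge of the arm causes in one arm at baseline and month 6. With visits at 0, 3 and 6 months and complete data, the fitted slope is (Y6 − Y0)/6, so the fitted 6-month change is Y6 − Y0. Hence:

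bias in the 6-month change = s6 − s0

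If time is categorical, the month-6 contrast gives the same result. The bias equals the whole baseline shift in size only when s6 = 0. It is zero when s6 = s0.

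**Size.** The documents give no value for s0, so 0.1 and 0.2 SD are assumptions. The share is taken of the planned 0.50, read as a difference in 6-month change.

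| s0 | Part persisting to month 6 | Size of bias | Share of 0.50 |
|---|---|---|---|
| 0.1 | none | 0.10 | 20% |
| 0.1 | half | 0.05 | 10% |
| 0.1 | all | 0 | 0% |
| 0.2 | none | 0.20 | 40% |
| 0.2 | half | 0.10 | 20% |
| 0.2 | all | 0 | 0% |

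**Effect on the test.** Completers per arm: 109 × 0.70 = 76.3. With correlation 0.5, the variance of Y6 − Y0 is 2 × (1 − 0.5) = 1, so SE = √(2/76.3) = 0.162 SD. By normal approximation:

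| Net bias (SD) | Type I error | Power for d = 0.50 if the bias opposes the intervention |
|---|---|---|
| 0 | 5.0% | 87% |
| 0.05 | 6.1% | 79% |
| 0.10 | 9.5% | 70% |
| 0.20 | 23.5% | 46% |

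A simulation used 109 per arm, an assumed 15% lost before month 3, 30% lost by month 6, and all available data. With a shift at baseline only of 0, 0.10 and 0.20 SD, type I error was 5.0%, 10.2% and 28.2%.

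**Participants randomised without a baseline.** G2 keeps participants in the mixed model when a time point is missing, so month 3 or month 6 data would still supply outcome rows. The gap is in the covariates: with demographics collected only at baseline, such a person would be dropped from a complete-case fit. The missing-data section plans both complete-case and multiple-imputation analyses but gives no rule for this group.

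**The case against.** The strongest reply is that the harmful order is inferred. The F2 paragraph mentions randomisation before it describes screening, so it is not a timeline, and its opening words can mean that consent is a precondition. J1a orders consent and baseline but does not mention randomisation. This stands as a limit: a reader might infer that the protocol expressly schedules randomisation before baseline, and it does not. But no other sentence corrects the literal reading.

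Second, the bias needs the participant to know the arm before answering DDS17, and nothing says when participants are told. Baseline is placed before the intervention, the evaluator has no access to assignments, and the peer's record described in Section K already holds a summary of baseline needs. Consent review and baseline may also share a call. All this makes early disclosure less likely. It does not rule it out, because nothing requires the allocation to be withheld.

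Third, a reader might infer that any baseline shift biases the result in full. That is one scenario. Participants still know their arm at months 3 and 6, and a shift that persists cancels.

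Fourth, a reader might infer that people without a baseline have no outcome rows and leave the analysis. G2's use of all available data contradicts that. Only the covariate problem remains.

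**Conclusion.** The point holds as a risk that the plan leaves open, not as a demonstrated bias. As written, F2 permits allocation, and its disclosure, before a self-reported baseline that is itself an outcome time in the primary model with a free difference between arms. Neither the preintervention label nor evaluator masking closes that gap.

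Its size depends on two things the documents do not give: whether participants learn their arm before DDS17, and how much of any shift remains at month 6. An assumed non-persisting shift of 0.1 to 0.2 SD would be 20% to 40% of the planned effect, with type I error of 9.5% to 23.5% under the stated approximation. Full persistence would bring the bias to zero. The documents therefore do not support saying that the primary test is invalid or that its error rate is inflated by a known amount. The change is still worth making, because it is nearly free and the problem could not reliably be repaired afterwards.

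**What to change.** Replace the sentence in F2 with wording such as: *Randomisation will follow informed consent and completion of the baseline assessment, using blocks of 6 or 8 stratified by referral source. The allocation will be released only after the baseline DDS17 has been recorded.*

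If practice already follows this order, the edit records it. If not, it changes the order of steps at enrolment. Either way it sets s0 to zero and ensures that everyone randomised has completed the baseline assessment. It does not address reporting differences at follow-up, which remain possible whenever participants know their arm.

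The cost is a short edit to F2 and to the enrolment procedure. It needs no extra visits or staff and does not change the sample size of 218.

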Peer intervention. The peer intervention will include approximately 5-6 contacts over a 3-month period. Peer coaches are responsible for providing emotional and social support, normalizing the difficulty of living with DM, modeling help-seeking behaviors, and connecting patients with VHA and/or Community-based Organizations (CBOs) to address mental health and DM self-management needs. Peer coaches are not responsible for health education directly, but will encourage patients to use appropriate programs in which mental health and DM self-management services are provided. They will be trained to offer encouragement and basic assistance with problem-solving, activation, achieving self-efficacy, and setting goals. As Veterans with DM or other chronic medical/mental health conditions, peer coaches are ideal guides who help uniquely by sharing their personal stories and modeling. After making an initial introduction by telephone, the peer coach will arrange to meet with the Veteran in person at a mutually suitable place (e.g. a coffee shop, a community agency, a VHA facility) or by telephone, Facetime, GoogleDuo, Zoom or Microsoft Teams with a VA cell phone. Home visits may be allowed for home-bound Veterans pending an evaluation of safety and approval of the PI/his designee. During this meeting, the peer coach will orient the Veteran to his or her role, exchange contact information and preferences for contact, and conduct a needs assessment to identify opportunities to recommend specific resources. Potential mental health resources include counseling and medication referrals, online or in-person support groups, and education materials about distress and mental health conditions. Potential DM resources include online education materials from the ADA, cooking and recipe information, referrals to DM education and dietitians, free and low-cost exercise classes and gyms, and local food banks that have DM-friendly foods. Specific resources for related issues--low-cost primary care clinics, help with sleep problems, and transportation resources for medical appointments--are included. Peer coaches will be trained to probe for additional information as needed and to identify specific unmet needs or experiences of securing help. For instance, a Veteran who reports feeling overwhelmed with a DM regimen may be asked other questions to identify whether he or she has obtained help from a health professional and what solutions have already been tried. As peer coaches come to understand the Veteran's priorities, preferences, and barriers better, they will provide validation and support, offer suggestions for a few applicable community programs, and facilitate goal setting to help the Veteran choose and follow through on recommendations. The peer coach will follow up by phone approximately every 2-3 weeks, based on Veteran needs and preferences. Information and education on DM self-management and psychological well-being may be provided verbally or through the mail and will be tailored to the patient's needs and preferences. Participants will also be provided with a study workbook and goal-setting worksheet. The intervention will end at 3 months, when the Veteran chooses to terminate or after 5 consecutive unsuccessful attempts at contact. To ensure fidelity to the intervention, peers will complete semi-structured session notes after each interaction with a Veteran that will be reviewed by the peer supervisor each week. Session notes will include which resources were provided, whether problem-solving or coaching was used, and progress towards goals.

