
We will develop a brief Memorandum of Understanding between the VA leadership team and each partner outlining: 1. The purpose/goals of the partnership, 2. What they can expect from the VA research team, and 3. What will be asked of them during the course of the project including activities, meetings, and surveys they will be asked to complete as part of the engagement process. Protection Against Risk: Questionnaires. Participants will be informed that if they do not wish to answer specific questions or wish to terminate the session, they will be able to do so.

Adverse Events. In addition to the subject's request, criteria for discontinuing a subject's participation may include, as determined by the Primary Investigator in discussion with the study team, any life-threatening or potentially disabling event, or hospitalization for acute medical or psychological illness. These serious adverse events (SAEs) will be recorded and included in the database. SAEs will be reviewed by the PI and reported to the IRB in accord with VAMC policy. Any subject who develops an SAE during the conduct of study protocols will be referred for immediate medical care at the VAMC or outside medical facility and referred to their physician for ongoing care. Management of Suicidal Ideation (SI) or Behavior. SI with intent or plan is an exclusion for this study. However, given that this is a study of treatment for distress, a plan for addressing suicidal behavior at any time during the study was developed (see section E2).

Section G: Sample Size/Data Analysis

G1. Sample Size

How many subjects (or specimens, or charts) will be used in this study?

Local: 218 Worldwide: 218

Please indicate why you chose the sample size proposed:

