Section H: Potential Risks/Discomforts

H1. Potential Risks/Discomforts

Describe and assess any potential risks/discomforts; (physical, psychological, social, legal, or other) and assess the likelihood and seriousness of such risks:

Overall, this study poses low risks to the Veterans. No deception is involved in any phase of the study, including the assessments and the intervention. Potential risks for the patients include 1) discomfort or negative response to the peer-led coaching and navigation intervention, 2) exacerbation of negative emotions at any point during the study period, 3) the disclosure of confidential material, and 4) fatigue or boredom related to the assessments.

a) Discomfort or negative response to the peer-led coaching and navigation intervention: The intervention will include scheduled breaks, during which the trained providers will discuss their assessments of individual participant's needs. Efforts will be made to engage all participants in a positive manner. Being in the study is optional thus all participants will be given the opportunity not to participate, stop the study at any time he/she likes, and ask questions at any time. Importantly, previous research has shown that similar interventions are effective at decreasing distress and enhancing quality of life.

b) Exacerbation of negative emotions: Some participants may not improve with the intervention or control condition or may experience an increase of distress-based symptoms that requires professional help. Those assigned to the control group may also experience an increase of distress-based symptoms. Alternative treatments are available to participants in the VA and community. These would include psychotropic medications and psychotherapy. Appropriate referrals will be made for participants who request it. In fact, all participants regardless of assignment will have resource and referral lists of clinical and non-clinical resources in the VA and community.

c) Disclosure of confidential material: Questionnaires and data will be labeled only with a participant identification number. Names will not be tied directly to the data. Patients will be informed that they do not need to answer any questions that they do not feel comfortable answering. Research staff will respect any requests by patients to not answer questions for the study.

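### SAEs are to be recorded, but no way of asking about them that is the same in both arms is described, and the peer arm has 7-8 planned post-baseline contacts against 2, so SAE counts by arm would lean towards the peer arm

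*Combined protocol and SAP*

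**What the plan says.** Section F2, Adverse Events, treats life-threatening or potentially disabling events and acute hospitalization as SAEs. It states "These serious adverse events (SAEs) will be recorded and included in the database" and "SAEs will be reviewed by the PI and reported to the IRB in accord with VAMC policy". It names no question, time point or source for learning of an event.

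The planned contacts after baseline, all from F2, are:

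- **Both arms:** "Patient assessments will be measured by telephone by an independent evaluator without access to group assignments at baseline, M3 and M6". The instruments listed cover distress, self-care, depression, anxiety, activation, self-efficacy and (baseline and month 6 only) self-reported use of resources. None is an SAE item.
- **Usual care:** "They will receive a packet of printed information that includes a list of self-management support resources in the VHA and the local community", with encouragement to see their own providers. No other follow-up contact is scheduled.
- **Peer arm:** "The peer intervention will include approximately 5-6 contacts over a 3-month period". The coach writes a note after each contact and a supervisor reviews the notes weekly. "Session notes will include which resources were provided, whether problem-solving or coaching was used, and progress towards goals".
- **Peer arm only, at month 6:** "We will administer a semistructured exit interview at M6 to intervention group participants". This may or may not be the same call as the assessment.

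Section G2 contains no analysis of SAEs. Sections E1 and H2 rate the study as minimal risk. Among the stated protections, H1 says "The intervention will include scheduled breaks, during which the trained providers will discuss their assessments of individual participant's needs".

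**The concern.** When events are not asked about in a fixed way, the number recorded depends on how often someone from the study speaks to the participant. Here that frequency differs by arm by design, and the extra channel (coach contact, note, weekly review) exists in one arm only. The extra contacts also come from people who know the allocation, whereas the evaluator does not.

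At stake is how SAE counts are read if they are shown by arm. An excess in the peer arm could be real or could come from better detection, and the data would not separate the two. A VA-records route would not settle it either: no such use is described for SAEs, and F1 makes recruiting Veterans who do not use the VHA central to the design.

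**Working it through.** The plan gives no figure to reproduce. The check has two parts: a count from the documents, and an illustration resting on stated assumptions.

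**1. Planned contacts after baseline**

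| Period | Peer arm | Usual care |
|---|---|---|
| Months 0-3, including the month 3 assessment | 5+1 = 6 to 6+1 = 7 | 1 |
| Months 3-6, including the month 6 assessment | 1 | 1 |
| Total | 7 to 8 | 2 |

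Ratio: 7/2 = 3.5 to 8/2 = 4.0. If the exit interview is a separate call, the totals are 8-9 against 2, a ratio of 4.0 to 4.5. All the coaching contacts fall in the first three months.

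**2. From contacts to recorded events**

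Assumptions, none from the documents: equal true risk in both arms; event times uniform over 6 months; every planned contact takes place; each contact after an event reveals it with probability q, the same for coach and evaluator. The chance that at least one of k contacts reveals the event is c(k) = 1 - (1-q)^k.

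*Usual care.* Half of events precede month 3 and meet 2 contacts; half follow it and meet 1.
U = 0.5·c(2) + 0.5·q. For q = 0.2: 0.5×0.36 + 0.5×0.20 = 0.280.

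*Peer arm.* Take n = 5 or 6 coaching contacts, evenly spaced.
- Spacing A, a gap before month 3: events in months 0-3 meet 2, 3, ..., n+2 contacts with equal chance.
- Spacing B, last coaching contact at month 3: they meet 3, ..., n+2 contacts.

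P = 0.5·mean c(k) + 0.5·q. For q = 0.2:
- A, n = 5: mean c(k) = 0.606, so P = 0.403 and P/U = 0.403/0.280 = 1.44.
- B, n = 6: mean c(k) = 0.685, so P = 0.443 and P/U = 0.443/0.280 = 1.58.

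| q | Usual care detects | Peer arm detects (A, n=5 to B, n=6) | Spurious ratio |
|---|---|---|---|
| 0.2 | 0.280 | 0.403 to 0.443 | 1.44 to 1.58 |
| 0.3 | 0.405 | 0.530 to 0.566 | 1.31 to 1.40 |
| 0.5 | 0.625 | 0.709 to 0.730 | 1.13 to 1.17 |
| 0.9 | 0.945 | 0.949 to 0.950 | about 1.00 |

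**3. In events.** With 218/2 = 109 per arm and an assumed true risk of 10%, each arm has 10.9 events. At q = 0.3 the record would show 10.9×0.405 = 4.4 in usual care and 10.9×0.530 = 5.8 to 10.9×0.566 = 6.2 in the peer arm: a spurious difference of about 1.4 to 1.8 events.

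**4. If coaches pick up or document less.** Let the evaluator's chance be 0.30 and the coach's 0.15. An event before j coaching contacts and both assessments is detected with probability 1 - 0.70²×0.85^j. Averaging as above gives ratios of 1.19 (A, n = 5) to 1.25 (B, n = 6). With a coach chance of 0 the ratio is 1.00. A coach chance above the evaluator's would raise it.

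**The case against.** **No planned analysis uses SAE counts.** G2 has no comparison by arm, and the stated use is case-by-case review and reporting to the IRB in a minimal-risk study. This stands, and it limits the point to SAE counts that may be reported by arm.

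**The plan does not say that events surface only by chance.** A reader might infer that an SAE is recorded only when a participant happens to mention it. That is inference from silence. The service-use questionnaire at month 6 goes to both arms and may contain a hospitalization item; its items are not shown. Section K lists health-record information among the research data. The Section S attachments and the coaches' manual are not in the text. Any of these could narrow the gap. None is linked to SAE recording in the text, and none removes the channel that only the peer arm has.

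**Four times the contacts is not four times the events.** A reader might infer a bias of that order, or a near-doubling by assuming that every event precedes every contact. The coaching contacts end at month 3, so later events meet one scheduled contact in each arm. This stands, and the timed model above allows for it.

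**Coaches may not write events down.** The listed note content has no place for an event, which weakens the claim that each coach contact counts as much as an evaluator call. This also stands; step 4 shows the effect. Coaching may also end early, which lowers the contact ratio.

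**Negative reactions to coaching have other routes.** Weekly supervision, the process diary, coach reflections and the exit interview could all pick them up, so it would be wrong to say that they go unobserved.

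**Conclusion.** The point holds as a matter of safety reporting. As written, the plan gives unequal opportunity to learn of SAEs: 7-8 planned contacts against 2, with the difference confined to months 0-3. The expected direction is over-recording in the peer arm at equal true risk. The size is modest and rests on assumption: a ratio of about 1.1 to 1.6 for a per-contact chance of 0.2 to 0.5, uniform event times and full delivery, approaching 1.0 when each contact is near certain to elicit the event.

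A reader might infer that the DDS17 comparison is biased too, because F2 allows the same events to lead to discontinuation. The documents do not support that. The wording is permissive, the decision rests with the principal investigator case by case, and nothing in the text lets an effect on follow-up be sized.

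The scheduled-breaks sentence in H1 is a separate and minor matter. It does not match the intervention in F2, where one coach meets or calls the Veteran, and it is not evidence of unequal ascertainment.

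**What to change.** At months 3 and 6, have the blinded evaluator ask every participant in both arms one fixed question, using the event terms of the Adverse Events paragraph and a fixed recall window (since the last assessment). Base any by-arm SAE summary on those answers, so that scheduled ascertainment is 2 against 2. List events learned through coaches separately. PI review and IRB reporting continue for events from any source.

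Cost: a minute or two on calls already scheduled, and a by-arm summary that leaves out events known only through coaches, which is why the separate list is needed.

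Separately and minor: add one field to the peer session note for events or negative reactions, and reconcile the scheduled-breaks sentence in H1 with the intervention described in F2.
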